In the GLP study, the occurrence of dose-dependent infusion-related reactions (IRRs) at 10 and 40 mg/kg (Days 15 or 22) resulted in early termination of dosing in these two dose groups with 2 monkeys in the 40 mg/kg group euthanized in extremis [a female on Day 15 (Dose 3) and a male on Day 22 (Dose 4)]. Minimally to moderately decreased platelets occurred at ≥10 mg/kg (Days 16 and 23) and transient, mild decreases in lymphocytes were seen in the 40 mg/kg group (both sexes on Days 2 and 16; 2 of 4 males on Day 23). Dose-dependent increases in splenic weight and increased lymphoid cellularity in the spleen and lymph node were noted and attributed to SL-172154 administration. These findings were reversed after a 4-week recovery period. Assessment of pharmacodynamic biomarkers showed that SL-172154 occupied CD40 and CD47 receptors on circulating blood cells and caused elevations in a number of serum cytokines. Transient and reversible complement activation was coincident with the production of ADA to SL-172154. Additionally, the presence of ADA from at least Day 15 (Dose 3) onward likely contributed to low or non-quantifiable plasma SL-172154 concentrations on Day 29. At the 1.0 mg/kg dose level, there were no clinical observations, abnormalities in clinical pathology parameters, or non-reversible pathology findings, thus 1.0 mg/kg was considered to be the no-observed-adverseeffect level (NOAEL) for intravenous infusion doses of SL-172154. The 1.0 mg/kg dose corresponded with mean Cmax and AUC_{0-last} values of 1230 ng/mL and 518 ng*h/mL on Day 1. The mean terminal elimination half-life $(t^{1/2})$ on Day 1 was approximately 0.4 hours following a 1 mg/kg dose and was higher with mean values of approximately 1.1 and 0.9 hours for the 10 mg/kg and 40 mg/kg dose groups, respectively.

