In vivo monkey PK data from the GLP toxicology study [Report_SL2020IB001] were used to convert the target Cmax to a human equivalent dose (HED). In the monkey GLP toxicology study, a dose of 1 mg/kg was associated with a mean Cmax of 1230 ng/mL (13.96 nM, n=6 monkeys). Note that the lowest dose studied in the GLP study was 0.1 mg/kg; however, the Cmax was not well characterized as only two animals had measurable concentrations at this dose level. The non-quantifiable concentrations were likely due to the rapid clearance of SL-172154 from the serum. Potential explanations for rapid drug clearance include an antigen sink due to the ubiquitous expression of CD47 on peripheral blood cells (i.e., RBC, platelets, PBMC) and target-mediated uptake at early time points with trafficking of cells (e.g., PBMC) and bound drug to peripheral tissues. From Day 15 onwards, the removal of drug by anti-drug antibodies results in rapid

CONFIDENTIAL Compound: SL-172154

clearance. Assuming dose-proportionality, a dose of 0.4 mg/kg in the monkey is predicted to achieve the preliminary human target Cmax (5.18 nM). The 0.4 mg/kg dose level in monkeys was converted to a HED using a standard conversion factor of 0.32 [FDA, 2005]. The resultant preliminary starting dose for IV infusion of SL-172154 in humans is 0.1 mg/kg (0.4 mg/kg x 0.32).

The GLP study concluded that 1.0 mg/kg was considered to be NOAEL for IV infusion doses of SL-172154. Thus, the proposed SL-172154 starting dose of 0.1 mg/kg is 1/10th the NOAEL dose of 1 mg/kg observed in cynomolgus monkeys and provides an appropriate safety margin for the FIH starting dose.

Justification for Schedule: A weekly dosing schedule for 5 consecutive weeks was implemented in the NHP studies. Toxicity was dose-dependent (only at the higher doses) and occurred at the third and subsequent doses. Receptor occupancy data from Day 1 (Dose 1) demonstrated that SL-172154 readily bound to its intended target in a dose-dependent manner, attaining >90% CD40 receptor occupancy on PBMCs and ~80% CD47 receptor occupancy on RBCs in the 10 and 40 mg/kg groups. Maximal occupancy for the CD47 receptor on RBCs was attained by 1 hour postinfusion and persisted through at least 168 hours. CD40 receptor occupancy was transient, likely influenced by endocytosis and migration of CD40+ cells to tissues including the spleen.

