4. ANALYSIS POPULATIONS

Population	Description
Screened	All subjects who have signed the main study inform consent form.
Screen Failures	All subjects who have signed the informed consent but have not received any dose of SL-172154.
All Treated	All subjects who receive at least one dose of SL-172154. Safety data will be evaluated based on this population.
DLT Evaluable	All subjects enrolled in the dose escalation cohorts 1) who have received ≥ 2 of the 3 scheduled doses of SL-172154 on Schedule 1 or who have received ≥ 2 of the 4 scheduled dose of SL-172154 on Schedule 2 during cycle 1 and completed the safety follow up through DLT evaluation period; or 2) who experienced any DLT during the DLT evaluation period. The DLT evaluation period is defined as the first 28 days. The DLT evaluable population will be used to guide dose escalation and to determine the MTD or MAD.
Response Evaluable	All subjects in the All Treated population who have a baseline disease assessment and have at least one post-baseline disease assessment or have progressed or died before the first post-baseline disease
PK Population	Subjects in the All Treated Population who have at least one postdose PK sample obtained and analyzed. The PK population will be used for the PK analysis.

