Categorical variables will be summarized by counts and by percentages of subjects in the corresponding categories. Percentages are routinely based on the total number of the specified population N if not otherwise specified. For frequency counts, categories whose counts are zero will be displayed for the sake of completeness. For example, if none of the subjects discontinue due to "lost to follow-up," this reason will be included in the table with a count of 0. Categories with zero counts will not have zero percentages displayed.

All confidence intervals (CIs) will be constructed at the 95% confidence level, unless specified otherwise.

All analyses and tabulations will be performed using SAS® v9.4 or above.

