Additional summaries for drug-related IRR AE (toxicity grade, seriousness, number of events, action taken) at event-level, at subject-level, and number of subjects with IRR at each dosing visit among the first two cycles and during all subsequent cycles combined will be provided.

All AEs, immune related AEs, drug-related AEs, Grade 3 or 4 AEs, drug-related Grade 3 or 4 AEs, DLTs, SAEs, fatal AEs, AEs leading to dose not given/held, infusion interruption, dose increased or dose reduced, and drug withdrawal, and infusion related reaction signs and symptoms will be presented in data listings. Pretreatment AE, defined as AEs that start prior to the first dose of the study treatment, will be flagged in relevant listings. All AEs for the Screen Failures population will also be presented in a data listing.

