	14.3.1.13.3	Treatment-Emergent Adverse Events Leading to Drug Interrupted by Preferred Term	All Treated
	14.3.1.14	Treatment-Emergent Adverse Events leading to Drug Withdrawn by Preferred Term	All Treated
	14.3.1.15	Summary of Drug-Related Infusion Related Reaction at Subject Level	All Treated
	14.3.1.16	Summary of Drug-Related Infusion Related Reaction at Event Level	All Treated
	14.3.1.17	Summary of Drug-Related Infusion Related Reaction by Dosing Visit	All Treated
	14.3.1.18	Deaths	
14.3.5		Laboratory	
	14.3.5.1	Hematology – Maximum CTCAE Grade Shift from Baseline	All Treated
	14.3.5.2	Chemistry – Maximum CTCAE Grade Shift from Baseline	All Treated
	14.3.5.3	Coagulation and Thyroid Function Test – Maximum CTCAE Grade Shift from Baseline	All Treated
	14.3.5.4	Laboratory Tests without CTCAE - Maximum Shift from Baseline with Respect to Normal Range	All Treated
	14.3.5.5	Post-Baseline Potential Serious Hepatoxicity	All Treated
	14.3.5.6	Summary of Change for Select Laboratory Tests	All Treated
14.3.6		Other Safety Data	
	14.3.6.1	ECOG Performance Status – Maximum Shift from Baseline	All Treated
14.3.7		PK	
	14.3.7.1	SL-172154 Serum Concentration-Time Data	PK
	14.3.7.2	SL-172154 PK Parameters	PK

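### The infusion-reaction-by-dosing-visit summary has no at-risk denominator, so under the SAP default undosed subjects dilute the later-visit rates

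*SAP*

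**What the plan says.** SAP 8.2 plans three summaries of drug-related IRRs: by event, by subject and by visit. For the last it promises that the "number of subjects with IRR at each dosing visit among the first two cycles and during all subsequent cycles combined will be provided". The sentence gives no denominator.

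The gap is filled by general rules elsewhere in the SAP:

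- SAP 5.2: "Categorical variables will be summarized by counts and by percentages of subjects in the corresponding categories".
- SAP 5.2, on the denominator: "Percentages are routinely based on the total number of the specified population N if not otherwise specified".
- SAP 13.1 lists Table 14.3.1.17, "Summary of Drug-Related Infusion Related Reaction by Dosing Visit", under the All Treated population.
- SAP 4 defines that population as "All subjects who receive at least one dose of SL-172154". Its N therefore stays the same at every visit.

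The toxicology background makes dose number relevant. Of the monkey studies, Protocol 3.2 says: "Toxicity was dose-dependent (only at the higher doses) and occurred at the third and subsequent doses".

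**The concern.** A subject can have an infusion reaction at a visit only if an infusion is started at that visit. Someone who has stopped treatment, or whose dose was held, is not at risk but still counts in a fixed N. Later percentages then mix two things: the reaction rate among those dosed, and the share still being dosed.

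This is the planned table that sets IRRs against successive doses, so it is where a reader would look for a change with repeated dosing. The SAP aims for about 6 to 12 subjects at the potential recommended dose. With so few, one or two undosed subjects move a percentage noticeably: 1 reactor among 4 dosed out of 6 treated is 1/4 = 25.0% of those dosed, but 1/6 = 16.7% of All Treated.

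The single entry for all cycles after the second has a further problem. It counts subjects with an IRR over any number of infusions, so it cannot be compared with the single-visit entries.

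**Working it through.** The documents state no IRR rate, drop-out rate or number dosed per visit, so there is no planned figure to reproduce. The rates and losses below are assumptions, shown as a range.

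**Formulas.** Let r_k be the per-dose IRR risk at the k-th dosing visit, and s_k the share of All Treated subjects who start an infusion there.

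- Percentage on All Treated = r_k × s_k
- Percentage on subjects dosed = r_k
- With a loss q per dosing visit, unrelated to reacting, s_k = (1 − q)^(k−1)

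**Visits.** On Schedule 1 the dosing visits in the first two cycles are C1D1, C1D8, C1D15, C2D1 and C2D15, so k runs from 1 to 5.

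**Constant risk of 30%, shown on All Treated (%):**

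| Loss per visit | C1D1 | C1D8 | C1D15 | C2D1 | C2D15 |
|---|---|---|---|---|---|
| 0% | 30.0 | 30.0 | 30.0 | 30.0 | 30.0 |
| 5% | 30.0 | 28.5 | 27.1 | 25.7 | 24.4 |
| 10% | 30.0 | 27.0 | 24.3 | 21.9 | 19.7 |
| 15% | 30.0 | 25.5 | 21.7 | 18.4 | 15.7 |

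For example, C2D15 at 10% loss is 30 × 0.9^4 = 30 × 0.6561 = 19.7. On subjects dosed, every cell would be 30.0.

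**Risk rising 20, 20, 30, 35, 40%, shown on All Treated (%):**

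| Loss per visit | C1D1 | C1D8 | C1D15 | C2D1 | C2D15 |
|---|---|---|---|---|---|
| 5% | 20.0 | 19.0 | 27.1 | 30.0 | 32.6 |
| 10% | 20.0 | 18.0 | 24.3 | 25.5 | 26.2 |
| 15% | 20.0 | 17.0 | 21.7 | 21.5 | 20.9 |

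A doubling by the fifth dose is damped at 5% and 10% loss and nearly invisible at 15%.

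**Whole subjects.** Take 12 treated, with 12, 12, 9, 6 and 6 dosed and 4, 4, 3, 2 and 2 reacting. On All Treated the table reads 33.3, 33.3, 25.0, 16.7 and 16.7%. On subjects dosed it reads 33.3% throughout. The bare counts, 4 falling to 2, mislead in the same way unless the number dosed stands beside them.

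**Later cycles combined.** SAP 3.4 allows up to two years of treatment, about 730/28 = 26 cycles. Cycles 3 to 26 are 24 cycles, or 24 × 2 = 48 infusions on Schedule 1 and 24 × 4 = 96 on Schedule 2. A subject in this entry may have had one infusion or dozens.

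**What a number-dosed denominator leaves.** Suppose 30% of subjects have a per-dose risk of 0.8 and 70% a risk of 0.1, and that a reactor leaves with probability 0.3.

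- At the first dose the rate is 0.3 × 0.8 + 0.7 × 0.1 = 31.0%.
- At the second, the dosed share is 0.3 × (1 − 0.24) + 0.7 × (1 − 0.03) = 0.228 + 0.679 = 0.907. The reacting share is 0.228 × 0.8 + 0.679 × 0.1 = 0.250. The rate among those dosed is 0.250/0.907 = 27.6%.
- Over five visits the rate is 31.0, 27.6, 24.6, 22.0 and 19.7% of those dosed, against 31.0, 25.0, 20.4, 16.9 and 14.2% of All Treated.

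No subject's own risk changed, yet both series fall. The better denominator removes only the dilution.

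**The case against.** The strongest reply has four parts.

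- **The by-visit sentence promises only a number.** SAP 8.1 and the overview summary in SAP 8.2 ask for percentages explicitly; this sentence does not. The SAP gives table titles but no shells, so a number-dosed row cannot be ruled out. This stands as far as it goes: the All Treated denominator is what the general rules yield, not something SAP 8.2 states. But nothing specifies another denominator, and counts without a number dosed have the same defect.
- **Early attrition may be small.** The first scheduled on-study scan is at about week 8, after the first two cycles. Entry requires ECOG 0 or 1 and a life expectancy above 12 weeks. This stands. At 5% loss per visit, a constant 30% still shows as 27.1% at the third dose.
- **The information is recoverable.** Total doses received are summarized, IRRs are also tabulated by subject and by event, and every infusion and IRR is listed. This stands too: no data are lost. None of these outputs puts a per-visit number dosed into this table.
- **Number dosed does not give the true risk.** Protocol 3.6.1 provides for permanent discontinuation after some reactions, and for premedication or slower infusion after others. This is right, and it limits what the fix can achieve.

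A reader might infer that the table will show reactions falling at the very doses where the monkey reactions began. The documents do not support that. An apparent fall follows when the per-dose rate is constant and subjects are lost, or when attrition outweighs a rise. In the rising example above, the step up at the third dose is still visible at every loss rate shown. The monkey signal was also confined to the higher doses, and Protocol 3.2 calls it unknown whether its contributing factors would occur in humans.

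**Conclusion.** The point holds as a reporting gap that should be closed. Under the SAP's own default, Table 14.3.1.17 would dilute later-visit IRR percentages by the share of subjects not dosed at each visit. The size cannot be fixed from the documents: for an assumed constant 30% rate, the understatement at C2D15 is 0, 5.6, 10.3 or 14.3 percentage points at 0, 5, 10 or 15% loss per visit (30 minus 30, 24.4, 19.7 and 15.7). These figures assume that loss is unrelated to reacting. The later-cycles entry cannot be interpreted without exposure beside it, whatever the attrition.

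A reader might also infer that dose-escalation decisions are at risk. They are not shown to be: SAP 3.2 and 5.1 base those on DLTs in DLT-evaluable subjects, and the Safety Monitoring Committee reviews available safety data about monthly. What is affected is how the reported table describes tolerability over repeated dosing.

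**What to change.** Add to SAP 8.2, and reflect in the shell for Table 14.3.1.17:

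- For each dosing visit in the first two cycles, show the number of subjects with a drug-related IRR over the number who started an infusion at that visit, with the percentage on the latter.
- For all later cycles combined, also show the number of subjects dosed, the number of infusions given and IRRs per infusion.
- Add a footnote that later-visit rates describe only subjects still being dosed, because those who react may stop treatment or receive premedication or slower infusions.

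The cost is a sentence or two in the SAP, a change to one table shell and a footnote. The administration data needed are already collected for the exposure summary and dosing listing in SAP 6.7. No trial procedure or clinical rule changes.

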8.3 Clinical Laboratory Evaluation

The clinical laboratory evaluation includes the following:

- Hematology: hemoglobin, hematocrit, platelet count, red blood cell count, white blood cell count, neutrophils, lymphocytes, monocytes, eosinophils and basophils.
- Clinical chemistry: blood urea nitrogen, creatinine, glucose, sodium, potassium, calcium, magnesium, phosphorus, total protein, albumin, lactate dehydrogenase, bicarbonate, haptoglobin, ferritin, C reactive protein and liver panel [alanine aminotransferase (ALT), aspartate aminotransferase (AST), total and direct bilirubin, and alkaline phosphatase (ALP)].
- Coagulation: prothrombin time, international normalized ratio, activated partial thromboplastin time, fibrinogen, and D-dimer.
- Thyroid: thyroid stimulating hormone and free thyroxine 4.

The clinical laboratory grades will be reported using the CTCAE v5.0. Separate listings will be provided for hematology, clinical chemistry, coagulation and thyroid tests. For each listing, baseline value will be specified for each subject.

Clinical laboratory results (hematology, clinical chemistry, coagulation, thyroid) will be summarized for worst case shift from baseline toxicity grade. Frequencies of maximum observed Grade 0-4 toxicity, as defined by the NCI CTCAE v5.0, will be presented for each laboratory parameter. The determination of the maximum grade post-baseline takes into account both planned and unscheduled assessments. Separate summaries indicating hyper- and hypo- directionality of change will be produced, where appropriate.

All laboratory values will be categorized as "low", "normal", or "high" relative to the normal ranges, or "unknown" if no valid result is available. For those laboratory parameters that do not have NCI CTCAE v5.0 grading criteria, worst case shift from baseline to post-baseline will be summarized. If a subject has worst case shifts to both "low" and "high", the subject will be counted in both categories.

Subjects with elevated worst post-baseline ALT, AST, total bilirubin, or ALP values that fall into the following categories will be identified and summarized:

• ALT in the categories of <=1x upper limit of normal range (ULN), >1x ULN, >3x ULN;

- AST in the categories of <=1x ULN, >1x ULN, >3x ULN;
- total bilirubin in the categories of <=1x ULN, >1x ULN, >2x ULN
- ALP in the categories of <=1x ULN, >1x ULN, >1.5x ULN, >2x ULN
- Potential Hy's law, defined as at least one case of post-dose total bilirubin > 2 x ULN occurred at the same day or after the first incidence date of ALT or AST > 3 x ULN post treatment.

Additionally, C1D2 change from C1D1, C1D16 change from C1D15, C2D2 change from C2D1, and C2D16 change from C2D15 will be summarized for select laboratory tests (hemoglobin, platelet, lymphocytes, neutrophil).

All laboratory results will be presented by subject in data listings.

8.4 Death

All death records will be presented in a data listing. Subject incidence of deaths within and outside of 30 days of last dose and the cause of death will be summarized.

8.5 Vital Signs and Pulse Oximetry

Vital signs (blood pressure, heart rate, respiration rate, temperature), body weight (with percent change from baseline) and pulse oximetry will be presented in a data listing.

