- Screening: Screening Period extends from Day -21 to Day -1. The following screening assessments must be performed within 72 hours of the first dose of SL-172154: hematology profile, chemistry profile, coagulation profile, ECOG score, physical exam, and pregnancy test. Baseline CT or positron emission tomography (PET)/CT or Magnetic resonance imaging (MRI) tumor assessments are required for all subjects within 28 days prior to the first dose of SL-172154. a.
- Assessment Window: With the exception of Screening assessments and unless otherwise specified, assessments performed at < 3-week intervals will have a +/- 3-day window and assessments performed at > 3-week intervals will have a +/- 1-week window. Assessments throughout the study are calendar based starting from the first day of dosing (day 1) in the first treatment period. Dose interruptions should not alter the assessment schedule for any subsequent treatment period. р.
- Inclusion/Exclusion criteria: Subjects must meet eligibility criteria prior to first dose of SL-172154 on C1D1. i
- Vital Signs: Blood pressure (BP), heart rate (HR), temperature (T) and respiratory rate (RR) must be measured after the subject has been sitting for at least five minutes (min). Pulse oximetry will be collected to coincide with vital sign time points noted below. d.
- and 15 min (\pm 5 min), 0.5 hour [hr] (\pm 5 min), 1 hr (\pm 10 min), 1.5 hr (\pm 10 min) 2 hr (\pm 10 min), 4 hr (\pm 10 min), and 6 hr (\pm 10 min) after start of Collect vital signs/pulse oximetry during Cycle 1 on D1, D8, D15 and Cycle 2 on D1 and D15: Predose (within 30 min of starting the infusion) infusion (SOI). 1
- Vital signs/pulse oximetry should be taken once prior to scheduled PK samples on C1D2, C1D3, C1D16 and C2D2 5
- Collect vital signs/pulse oximetry on dosing days \geq C3D1: Predose (within 30 min of starting the infusion) and at the end of infusion [EOI] (± 2 mm) 3)
- within 72 hrs of starting SL-172154. Repeat this test every 8 weeks during SL-172154 treatment (i.e., C3D1, C5D1, C7D1, etc.). Contraception should be Pregnancy Test: A serum pregnancy test (beta-human chorionic gonadotropin [β-hCG]) or urine pregnancy test must be performed at screening for all FCBP continued for at least 30 days after the last dose of SL-172154. e.

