6.4.4 Vital Signs

Vital signs will be assessed in a semi-supine position at rest and will include temperature (T), systolic and diastolic blood pressure (BP), heart rate (HR), and respiratory rate (RR). BP and RR measurements should be preceded by at least 5 min of rest for the participant in a quiet setting without distractions. Refer to footnote "d" in the SOA tables for details on when to collect vital signs.

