2. STUDY OBJECTIVES AND OUTCOME MEASURES

Objective	Outcome Measure	
Primary Objectives		
To evaluate the safety and tolerability of SL-172154 and to identify the maximum tolerated dose (MTD) or maximum administered dose (MAD) of SL-172154 in subjects with platinum-ineligible ovarian, fallopian tube, or primary peritoneal cancers	■ Safety/tolerability outcomes include: incidence of all adverse events (AEs) and immune-related adverse events (irAE), serious adverse events (SAEs), fatal SAEs, dose limiting toxicity (DLT), AEs and irAEs leading to discontinuation, and changes in safety assessments (e.g., laboratory parameters, vital signs etc.) per National Cancer Institute Common Terminology Criteria for Adverse Events (NCI-CTCAE – version 5.0). ■ The MTD is defined based on the rate of DLTs and the MAD is the highest dose administered.	
Secondary Objectives		
To select the recommended Phase 2 dose (RP2D) for SL-172154.	 Based on review of all data collected during dose escalation, dose expansion, and pharma- codynamic cohorts including safety, 	

	tolerability, pharmacokinetic (PK), anti-tumor
	activity, and pharmacodynamic effects.
To assess preliminary evidence of anti- tumor activity of SL-172154	Disease assessment per investigator assessment according to Response Evaluation Criteria in Solid Tumors version 1.1 (RECIST v1.1). ■ Objective response rate (ORR) (proportion of subjects whose best response is a complete response [CR] or partial response [PR]) ■ Clinical benefit rate (CBR): proportion of subjects whose best overall response is a CR, PR or stable disease (SD) ≥ 16 weeks ■ Time to response (TTR): time from the first dose until the first response (CR or PR, whichever is recorded first) that is subsequently confirmed ■ Duration of response (DOR): time between first response (CR or PR, whichever is recorded first) that is subsequently confirmed and date of disease progression
To evaluate immunogenicity to SL-172154 during and after treatment.	 Number/proportion of subjects with positive ADA titer ADA duration Transient vs. persistent ADA
To characterize the pharmacokinetics (PK) of SL-172154.	 Maximum observed concentration (Cmax) and time at which the maximum concentration is observed (Tmax) and minimum observed concentration (Cmin) following single and multiple doses of SL-172154 Area under the serum concentration-time curve (AUC) Terminal elimination half-life (t½), Clearance (CL) and Volume of Distribution (Vz)
Exploratory Objectives	

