5.2 Reporting Conventions

The statistical analyses will be reported using summary tables, figures, and data listings. The International Conference on Harmonisation (ICH) numbering convention will be used for tables, listings, and figures.

Data from all participating sites will be pooled prior to data summary or analysis. It is anticipated that subject accrual will be spread thinly across sites and summaries of data by site will not be informative and therefore, will not be provided.

Unless specified otherwise, all summary tables will be presented by dose schedule/level for all subjects in the analysis population, and subjects from dose escalation, pharmacodynamic and dose expansion cohorts will be pooled. Summaries will also be provided for subjects at the same dose level pooled across schedules. Select safety summary tables may be provided for the dose escalation cohorts.

All individual subject data listings will be presented by dose level, dose schedule and subject, unless specified otherwise. Data from all assessments, whether scheduled or unscheduled, will be included in the listings. Listings will present the data in their original format (without any imputation), unless specified otherwise.

Summaries by planned time point will include data from scheduled assessments and all data will be reported according to the nominal visit for which it will be recorded (i.e., no visit windows will be applied). Unscheduled data, when summarized, will be included only in calculation of the maximum or minimum value over time such as worst-case post-baseline. If multiple assessments are reported on the same date for the same scheduled planned time, the worst-case result will be analyzed.

Continuous variables will be summarized with means, standard deviations, medians, minimums, and maximums. The precision of the original measurements will be maintained in summaries and listings, when possible. Generally, means and medians will be presented to one more decimal place than the raw data, and the standard deviations will be presented to two more decimal places than the raw data.

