	16.2.7.8	Immune Related Adverse Events	All Treated
	16.2.7.9	Infusion Related Reaction Adverse Events	All Treated
	16.2.7.10	Adverse Events Leading to Infusion Interrupted	All Treated
	16.2.7.11	Adverse Events Leading to Dose Increased or Dose Reduced	All Treated
	16.2.7.12	Adverse Events Leading to Dose not given/Held	All Treated
	16.2.7.13	Adverse Events Leading to Drug Withdrawn	All Treated
	16.2.7.14	Infusion Reaction Signs and Symptoms	All Treated
	16.2.7.15	Death	All Treated
	16.2.7.16	All Adverse Events for Screen Failure Subjects	Screen Failure
16.2.8		Individual Laboratory Measurements	
	16.2.8.1	Hematology	All Treated
	16.2.8.2	Clinical Chemistry (including ferritin and haptoglobin)	All Treated
	16.2.8.3	Coagulation and Thyroid Function	All Treated
16.2.9		Listing of other safety data	
	16.2.9.1	Vital Signs and Pulse Oximetry	All Treated
	16.2.9.2	ECOG Performance Status	All Treated
	16.2.9.3	Cardiac Assessments: ECG	All Treated
	16.2.9.4	Cardiac Assessments: ECHO	All Treated
	16.2.9.5	Blood Phenotyping and Direct Antiglobulin Test	All Treated
	16.2.9.6	Transfusions	All Treated

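### Changes in vital signs are named within the primary safety outcome, but the SAP plans only a listing, with no summary of change from predose by dose; separately, the protocol gives two postures for the readings

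*SAP*

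**What the plan says.** **Outcome.** SAP Section 2 (matching Protocol Section 2 and the synopsis) puts under the primary objective "changes in safety assessments (e.g., laboratory parameters, vital signs etc.) per National Cancer Institute Common Terminology Criteria for Adverse Events".

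**General rule.** Protocol 9.2.3 says continuous variables will be summarized with descriptive statistics. Protocol 9.2 says departures from the analyses described in the protocol will be documented in the SAP and the final report.

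**Planned analysis.** SAP 8.5 is one sentence: vital signs, "body weight (with percent change from baseline) and pulse oximetry will be presented in a data listing". Percent change is attached to body weight alone. In SAP 13.1 the heading for other safety data holds a single table, "ECOG Performance Status – Maximum Shift from Baseline". SAP 13.2 has no vital-sign figure. The only output is listing 16.2.9.1, "Vital Signs and Pulse Oximetry". The four changes in SAP Section 11 concern pooling of cohorts, the DLT evaluable population, the screened population and the PK population.

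**Collection.** Footnote d of both schedule-of-assessments tables requires readings before the infusion and at seven times up to 6 hours after its start, on most dosing days of cycles 1 and 2.

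**Posture.** Footnote d says that blood pressure, heart rate, temperature and respiratory rate "must be measured after the subject has been sitting for at least five minutes (min". Protocol 6.4.4 says "Vital signs will be assessed in a semi-supine position at rest", and refers to footnote d only for timing.

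**The concern.** Infusion reactions and cytokine release are the risks the protocol singles out (1.4.1 and 5.1.5). Its guidance in 3.6.1 names changes in heart rate and blood pressure as signs of an infusion reaction, and hypotension as a feature of cytokine release. The vital-sign series around each infusion is the objective record of those effects. As planned, it reaches a summary only when a site reports an adverse event. A pattern of moderate, unreported falls that grew with dose would have to be found by reading rows and subtracting by hand.

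The SAP handles similar data differently. Section 8.3 summarizes next-day change from dosing day for hemoglobin, platelets, lymphocytes and neutrophils, and worst-case laboratory shifts. Section 8.7 summarizes worst-case ECOG shift.

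The posture conflict is a separate matter of data quality. Sites could follow either instruction, which would add variation, mainly to blood pressure and heart rate, that has nothing to do with the drug.

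**Working it through.** The plan gives no figure to reproduce. The check is a comparison of passages plus a count of the readings affected.

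**1. Is a change in vital signs derived or summarized anywhere?**
- SAP 8.5: listing only; change is derived for body weight only.
- SAP 13.1 and 13.2: no vital-sign table or figure.
- SAP 5.3.2: the default baseline is the last value on or before the first dose in cycle 1. No same-day predose reference is defined for later infusions.
- SAP 8.2: infusion-reaction summaries are made at subject level, event level and by dosing visit, but they count drug-related adverse events, not measurements.

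So no planned output shows change in vital signs from predose by dose.

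**2. How many readings does this concern?**
- Time points per intensive day (footnote d): predose, 15 min, and 0.5, 1, 1.5, 2, 4 and 6 hours after start = 8.
- Schedule 1 intensive days: C1D1, C1D8, C1D15, C2D1, C2D15 = 5, so 5 × 8 = 40 sets per subject.
- Schedule 2 intensive days: C1D1, C1D8, C1D15, C1D22, C2D1, C2D8, C2D15 = 7, so 7 × 8 = 56 sets per subject.
- Planned size (SAP 3.3): 33 subjects if only Schedule 1 is evaluated; 54 if both are, made up of 21 escalation subjects per schedule and 12 in the pharmacodynamic and expansion cohorts.

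| Case | Calculation | Sets |
|---|---|---|
| 33 subjects, Schedule 1 only | 33 × 40 | 1,320 |
| 54 subjects, the 12 on Schedule 1 | 33 × 40 + 21 × 56 = 1,320 + 1,176 | 2,496 |
| 54 subjects, the 12 on Schedule 2 | 21 × 40 + 33 × 56 = 840 + 1,848 | 2,688 |

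The allocation of the 12 is an assumption, as is completion of cycles 1-2 by every subject. Early discontinuation would lower all three counts.

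**3. What can a table support?**
- Outside the intensive days (C2D22 on Schedule 2, and dosing days from C3D1) only predose and end-of-infusion readings are taken, so the table must stop at the days listed above.
- Times run from the start of infusion. The planned infusion at 0.1 to 1.0 mg/kg is 30 minutes. The clarification memos cited under SAP Table 1 lengthened it to 120 minutes at 3 and 10 mg/kg. The 6-hour series then covers 6 − 0.5 = 5.5 hours after the end of a 30-minute infusion and 6 − 2 = 4 hours after a 120-minute one.
- Premedication is required at 10 mg/kg or higher and discretionary below (Protocol 5.1.2.3).
- Escalation plans about 21 subjects over five levels per schedule, 21 / 5 ≈ 4 per level.

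**The case against.** The strongest reply is that the SAP already lets infusion effects be seen by dose. SAP 5.2 states: "All individual subject data listings will be presented by dose level, dose schedule and subject, unless specified otherwise". Reported infusion reactions are tabulated (14.3.1.15 to 14.3.1.17), and SAP Section 8 lays out safety summaries by schedule and dose level. This stands. A reader might infer from the listing-only plan that no infusion-related change can be read by dose, and the documents do not support that. What is missing is a tabulated change.

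A reader might also infer that the posture conflict prevents comparison across doses. Nothing ties posture to dose; the conflict adds variation, and whether posture changed within any subject is unknown.

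Vital signs are only an example within a broad safety outcome, and Protocol 9.2.4 promises no vital-sign table. That is fair, but SAP Section 2 repeats the example, and the general rule in Protocol 9.2.3 covers continuous variables without exempting them.

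The harm is conditional: the protocol tells sites to record any toxicity as an adverse event (7.1.1), and the safety committee reviews available data monthly. This lowers the weight of the point. It does not remove it, because a measured series is useful precisely as a check that does not depend on site reporting.

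With about four subjects per level, individual listings are a defensible main display. That argues for a simple descriptive table and against tests or thresholds.

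**Conclusion.** The point holds as a reporting gap. A measure named within the primary safety outcome is listed but not summarized, contrary to the general rule in Protocol 9.2.3, and SAP Section 11 does not record the departure. The readings affected number 1,320 for 33 subjects on Schedule 1 and 2,496 to 2,688 for 54 subjects on the planned split, under the assumptions shown. Multiplying all 54 subjects by 56 would give 3,024, but 54 is reached only with about 21 escalation subjects on Schedule 1, so that figure does not fit the plan. The counts show how much would have to be read by hand; they do not show that a signal would be missed.

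Dose escalation and the MTD rest on DLTs and are not affected by this gap. The two posture passages contradict each other and must be reconciled; that conflict stands on its own and does not enlarge the first point.

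**What to change.** **SAP 8.5 and 13.1.** Add one descriptive table by schedule and dose level, limited to the intensively sampled infusion days (Schedule 1: C1D1, C1D8, C1D15, C2D1, C2D15; Schedule 2: C1D1, C1D8, C1D15, C1D22, C2D1, C2D8, C2D15). Show change from that day's own predose value, and the worst value after the start of infusion: lowest systolic blood pressure and oxygen saturation, highest heart rate and temperature. Define the same-day predose reference explicitly, since the default baseline in SAP 5.3.2 does not supply it. Footnote that infusion duration and premedication differ by dose level. No cut-off limits are needed.

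If the sponsor prefers listings only, SAP Section 11 should say so and give the reason.

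**Protocol.** Reconcile footnote d of both schedule tables with Section 6.4.4 so that one posture is stated. If collection is already complete, rewording will not repair the readings, and the inconsistency should be reported as a limitation.

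**Cost.** One extra table from data already collected and one wording correction. The downside is sparse cells, at about 3 to 6 subjects per dose level, so the table should be read as description alongside the listing.
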